3.3.2 Secondary Outcome Measures

No significant change in UEFI, or 9HPT from baseline to 24 months. Exploratory measures: correlations between change in TEMPA/UEFI/9HPT scores and FSS, MUSIQOL and SDMT values from baseline through 24months after treatment initiation with Ocrevus[™].

3.4 SAFETY PLAN

Patients will be evaluated at each study visit for the duration of their participation in the study for any new adverse events (AEs), especially for those that may interfere with the testing or commercial dosing schedule.

3.5 COMPLIANCE WITH LAWS AND REGULATIONS

This study will be conducted in accordance with current U.S. Food and Drug Administration (FDA) Good Clinical Practices (GCPs), and local ethical and legal requirements.

4.0 MATERIALS AND METHODS

This is a 24-month, prospective, observational study which will be conducted at the University of South Florida (USF) MS Center. On average 80-100 patients a week are seen at the study site. This large patient population offers a suitable number of potential candidates in order to meet the enrollment goal. This study will be conducted in adult multiple sclerosis patients who have upper extremity impairment and must satisfy the approved therapeutic indication for Ocrevus[™]. Decision to treat with Ocrevus[™] must precede enrollment. We anticipate enrollment will be random and open to any patient that meets the criteria below which will aid in the evaluation of our results to the general MS population. The targeted population are those patients that more often rely on their upper extremity function for activities of daily living due to impairment in other systems such as gait.)

Every effort to maintain consistency (by use of the same rater) for the administration of the upper extremity assessments will be made. The same instructions for the patient questionnaires will be given at each time point.

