4.1.3 Exclusion Criteria

Candidates will be excluded from study entry if any of the following exclusion criteria exist at the time of study entry:

- Severe weakness in bilateral upper limbs causing complete loss of function
- History of severe allergic or anaphylactic reactions or known drug hypersensitivity
- Female subjects considering becoming pregnant while in the study
- Female subjects who are currently pregnant or breast-feeding
- Unwillingness or inability to comply with the requirements of the protocol including the presence of any conditional (physical, mental or social) that is likely to affect the subject's ability to comply with the protocol.
- Active HBV infections
- Prior treatment with Ocrevus™
- Severe tremor/ataxia of the UE as defined by an EDSS with Cerebellar Functional System score of 3 or more due to upper extremity score (moderate tremor or clumsy movements interfere with function in all spheres)

- Severe spasticity of the UE as defined by EDSS, Pyramidal Functional System score- Upper Limb spasticity subscore of 3 or more (severely increased muscle tone that is extremely difficult to overcome and full range of motion is not possible)
- Cognitive impairment that may interfere with the conduct of the necessary testing (determined by the investigator)
- Any other reason that, in opinion of the Investigator and/or the Sponsor, the subject is determined to be unsuitable for enrollment in this study

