4.9.3 Efficacy Analysis

a. Primary Endpoint

1. TEMPA scores after 24 months of Ocrevus[™] treatment. Paired sample t-test to compare the 24 month measurements to the baseline measurements.

Mean within-patient changes from baseline through 24 months (TEMPA). Oneway repeated measures ANCOVA for TEMPA scores from baseline, 6 months, 12 months, 18 months, 24 months which will account for baseline characteristics (baseline disability level). A soft stratification will be applied so that recruitment will aim to include a spread of types of patients, those below overall EDSS of 6.0 and those above 6.0. If more than 2/3 of total enrollment is in one of the categories, the study team will reestablish efforts to recruit for the other cohort.

If data does not have normal distribution, then other non-parametric analysis will be employed (such as sign test for TEMPA functional score).

The threshold to determine a significant clinical change will be >20% from baseline value. This clinically significant difference is estimated based on data from the Oratorio trials that showed progression among both groups (placebo and OcrevusTM) but to a lesser extent in the OcrevusTM arm with an established clinically significant threshold of 20% (data will be requested from sponsor for use to review 9HPT results for the abnormal function at baseline group of patients). Measures will be collected and analyzed as units of time (seconds) and as functional scores on an ordinal scale that range from 0 to -3 (0 indicating

no signs of dysfunction).Ad hoc analysis may occur that includes evaluation of patients with significant clinical changes versus those that did not have significant clinical change based on any of the subscales within the TEMPA or physical exam. We will review >15%, >20% and >25% [in better hand and in worse hand] change from baseline with increases in time implying clinical progression and stability or decrease in time implying stability or improvement in function

b. Secondary Endpoints

Pearson correlation coefficients will be calculated to evaluate correlations between UE function (measured by TEMPA and 9HPT) primarily at baseline but also at each time point over the 24-month time period to compare patient responses on the UEFI, FSS, and MUSIQOL. Correlations with the primary endpoint scores and the SDMT will also be analyzed for any indication of new cognitive impairment that may interfere with the interpretation of the results.

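### Section 4.0 calls enrolment random and links it to the general MS population, but the design is a single-centre non-probability sample whose results apply only to patients like those enrolled

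*Combined protocol and SAP*

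**What the plan says.** Section 4.0 describes a "prospective, observational study which will be conducted at the University of South Florida (USF) MS Center". It goes on: "We anticipate enrollment will be random and open to any patient that meets the criteria below", and attaches a benefit to this, "which will aid in the evaluation of our results to the general MS population". The same section says that the decision to treat with Ocrevus "must precede enrollment", and then names a narrower group: "The targeted population are those patients that more often rely on their upper extremity function for activities of daily living".

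Section 4.1.1, Subject Selection, is a heading with no text. Section 4.1.2 requires EDSS 4.0-8.0 and weakness in at least one upper limb. Section 4.1.3 excludes patients with conditions likely to affect compliance, patients whose cognitive impairment the investigator judges may interfere with testing, and finally "Any other reason that, in opinion of the Investigator and/or the Sponsor, the subject is determined to be unsuitable for enrollment in this study".

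Section 4.9.3 adds: "A soft stratification will be applied so that recruitment will aim to include a spread of types of patients". The two groups lie below and above EDSS 6.0. If more than 2/3 of enrolment falls in one of them, "the study team will reestablish efforts to recruit for the other cohort".

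Section 4.9.6 expects 30 patients to be eligible, plans data on 30 and allows up to 35 to be screened. It gives the percentage remaining within 20% of baseline as an aim. The primary analyses named in section 4.9.3 are a paired t-test and a repeated-measures ANCOVA of TEMPA. There is one group (section 4.9.2).

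**The concern.** Random enrolment has a definite meaning: each member of a defined population has a known chance of entering, so the sample estimate carries over to that population. Section 4.0 claims the property and draws the inference, but no section supplies the mechanism.

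This matters more than it would in a randomised trial. A between-group comparison keeps its internal validity when the sample is unrepresentative. Here there is no comparator, so a proportion stable, or a mean change, depends directly on who enters. Section 3.2 says the study is meant to help prescribers answer patients' questions, so the population to which the answer applies is part of the result. The same section says ORATORIO cannot be fully extrapolated to this study's patients because its own patients differed. That reasoning equally limits extrapolation from this study to MS in general.

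No section asks for a record of eligible patients who were not invited, declined, or were excluded on judgement. Reporting the baseline characteristics of those enrolled (sections 4.9.1 and 4.9.2) shows who came in, but not who did not.

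**Working it through.** There is no stated figure to reproduce, since section 4.9.6 says the sample size was not calculated. The check is a comparison of sections, followed by illustrations. **Every stable rate, selection ratio and EDSS mix below is an assumption; the documents give none.**

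**1. The claim against the design**

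- Random entry (4.0): no sampling frame, random draw or consecutive rule anywhere, and 4.1.1 is empty.
- Random read loosely as unselected: the steering at EDSS 6.0 (4.9.3) and the judgement exclusions (4.1.3) do not fit this reading either. The steering starts when more than 2/3 × 30 = 20 of 30 patients are in one group.
- General MS population (4.0): entry needs a prior decision to treat, EDSS 4.0-8.0 and arm weakness, at one centre.

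The sample is therefore a non-probability sample from a restricted population.

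**2. How much room there is for selection**

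Inputs from 4.9.6: 30 expected eligible, 30 planned, up to 35 screened. Assume 80% stable among those enrolled (24 of 30) and 60% among eligible patients missed.

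- 30 eligible, all enrolled: no shift.
- 35 eligible, 5 missed: (24 + 0.6 × 5)/35 = 27/35 = 77.1%, a shift of 2.9 points.
- 60 eligible, 30 missed: (24 + 0.6 × 30)/60 = 42/60 = 70.0%, a shift of 10 points. This needs twice the number that 4.9.6 expects.

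**3. Selection related to outcome**

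Let p be the true stable proportion among eligible patients and r the relative chance of enrolment of those who will stay stable. The sample shows p·r/(p·r + 1 − p). With p = 0.70:

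- r = 0.8: 0.56/0.86 = 65.1%
- r = 1: 70.0%
- r = 1.25: 0.875/1.175 = 74.5%
- r = 1.5: 1.05/1.35 = 77.8%
- r = 2: 1.40/1.70 = 82.4%

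Nothing in the documents fixes r, or says whether it is above or below 1.

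**4. Steering at EDSS 6.0**

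Let w be the share below 6.0. Pooled stable rate = w × (rate below) + (1 − w) × (rate above).

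- Rates 80% and 60%, source w = 0.8: 0.64 + 0.12 = 76.0%. At the 2/3 limit 73.3%; at 50/50 70.0%.
- Rates 90% and 50%, source w = 0.8: 82.0%, 76.7% and 70.0% in turn.
- Rates 80% and 60%, source w = 0.2: 0.16 + 0.48 = 64.0%. At the opposite limit (w = 1/3) 66.7%.
- Equal rates in the two groups: no shift.

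Steering can lower the pooled percentage, raise it, or leave it unchanged.

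**5. Sampling error**

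Exact 95% intervals for n = 30: 21/30 (70%) gives 50.6% to 85.3%; 24/30 (80%) gives 61.4% to 92.3%. These are wide beside most of the shifts above, but they describe chance variation only and make no allowance for selection.

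**The case against.** The strongest reply is that this is loose wording in a self-described pilot. The protocol only anticipates random enrolment, says only that it will aid evaluation, and names a narrower target group in the next sentence. If about 30 patients are eligible and 30 are enrolled, nearly everyone eligible is in the study. The EDSS rule aims at a spread and turns no one away in terms, and the ANCOVA is to account for baseline disability.

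Much of this stands, and it limits the size of the point. It does not supply the missing method. The expectation of 30 may prove wrong, and without a log nobody could tell. The ANCOVA adjustment does not reach the percentage stable or any selection on other characteristics.

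Several stronger readings are tempting, and the documents do not support them:

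- **That patients are hand-picked, or that staff choose whom to approach.** No section describes how patients are approached. Enrolment is stated to be open to all who qualify.
- **That clinic traffic shows wide room for choice.** 80-100 patients a week is 80 × 52/12 = 347 to 100 × 52/12 = 433 contacts a month. These include repeat visits and ineligible patients, so they do not count eligible ones.
- **That the bias inflates stability.** Nothing links fitness to attend visits with TEMPA stability, and steps 3 and 4 of the working show shifts in either direction.
- **That section 4.2 contradicts section 4.0.** Its statement about randomisation concerns treatment assignment.
- **That the percentage stable is the sole result.** The named primary tests are of TEMPA change.

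**Conclusion.** The point holds as a fault in the stated inference. Section 4.0 claims random enrolment and uses it to reach towards the general MS population, while the design is a single-centre, non-probability sample of patients already chosen for Ocrevus, with restricted eligibility, discretionary exclusions and steered recruitment. The percentage stable and the mean TEMPA change both apply only to patients like those enrolled.

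The bias cannot be sized or signed from the documents. On the protocol's own expectation of about 30 eligible patients it may be nil or small: 2.9 points if five of 35 eligible patients are missed, under assumed rates of 80% and 60%. A 10-point shift would need about 60 eligible patients under the same rates. No stated calculation changes. Judgement exclusions and a planned EDSS spread are legitimate. The fault is in calling the result random and leaving selection unrecorded. Because the study has no control arm, the correction changes what it may conclude and is worth making.

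**What to change.** - **Section 4.0, method of entry.** Replace random enrolment with consecutive invitation of every patient for whom Ocrevus has been chosen and who meets 4.1.2 and 4.1.3. The empty section 4.1.1 is the natural place for the detail.
- **Section 4.9.3, steering.** State that it adds outreach to the under-represented EDSS group and turns no eligible patient away, so that it is compatible with consecutive invitation. Say which group an EDSS of exactly 6.0 belongs to, since the text covers only below and above.
- **Log.** Keep prospectively, and report, one line per patient for those eligible, invited, declined and excluded on judgement, with age, EDSS, MS form and reason. The discretionary exclusions can stay if they are recorded here.
- **Section 4.0, inference.** Replace the general MS population with patients starting Ocrevus at this centre with EDSS 4.0-8.0 and upper-limb weakness.

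The cost is a few sentences of protocol text, minor clerical work and a narrower stated claim. The log should start with the first patient, because it is hard to reconstruct reliably afterwards.

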4.1 SUBJECTS

4.1.1 Subject Selection

4.1.2 Inclusion Criteria

To be eligible for entry into this study, candidates must meet all of the following eligibility criteria at the time of study entry:

- Must give written informed consent and any authorizations required by local law (e.g., Protected Health Information [PHI])
- Aged 18-70 at the time of informed consent
- Must have a relapsing or progressive form of MS
- Male subjects and female subjects of child-bearing potential (including female subjects who are not post-menopausal for at least 1 year) must be willing to practice effective contraception (as defined by the investigator) during the study and be willing and able to continue contraception for 6 months after their last dose of study treatment
- EDSS 4.0-8.0
- UE weakness in at least one limb, defined as grade 4/5 in ≥ 2 muscles per limb
- Muscle weakness must be primarily related to MS
- Joint ROM must be within functional limits
- Patient must be able to perform 9HPT and TEMPA tests with at least one limb

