2. OBJECTIVES

2.1 PRIMARY OBJECTIVES

To measure for clinical stabilization (defined as no significant change (≤20%) from baseline of UE function in multiple sclerosis patients with upper extremity impairment treated with Ocrevus[™].

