The TEMPA scale is composed of nine standardized tasks which represents activities of daily living. Four items are unilateral (pick up and move a jar; pick up a pitcher and pour water into a glass; handle coins; pick up and move small objects) and five bilateral tasks (open a jar and take a spoonful of coffee; unlock a lock and open a pill container; write on an envelope and stick on a stamp; shuffle and deal playing cards; put a scarf around one 's neck). The outcome parameters used in this study are speed of execution (seconds) and the functional rating. The functional rating refers to the participant's independence in each task measured on a four-level scale: (0) successfully completed without hesitation or difficulty; (-1) completed, but with some difficulty; (-2) partially executed or some steps were performed with significant difficulty; and (-3) not completed, even if any degree of assistance was offered. A total score will be determined by adding the scores obtained for both the unilateral and bilateral tasks. Individual analysis of the unilateral and bilateral scores will be conducted to evaluate for functional improvement in the affected UE. Scores typically range from 0 to -50, with higher scores representing better performance. [12] The UE function will be measured by a consistent rater that is trained and qualified (must be a MD or equivalent).

The 9HPT is an objective measure of manual dexterity, which is incorporated into the MSFC, is a widely used measure across most clinical trials in multiple sclerosis populations. The time to completion is measured twice on both the dominant and non-dominant hand. For this study purpose will also record the "better" and "worse" limb so that the data can be cautiously compared to prior studies completed in multiple sclerosis patients. The task of the 9HPT is for the patient to pick up each individual peg, one at a time, and place it in the board (that has the same number of peg holes for each peg). Once all the pegs are placed in the peg holes the patient then removes each peg, again one at a time, placing them back into the peg bowl from which they were originally located. Although this measure has been used in several multiple sclerosis trials due to its ease of administration, there are many other factors of upper extremity function that are not being assessed that can be captured by the TEMPA.

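### An arm already at the TEMPA functional floor can be enrolled; its own functional score cannot worsen, and it loosens the 20% rule on the total score

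*Combined protocol and SAP*

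**What the plan says.** **Entry.** Section 4.1.2 defines the qualifying weakness as "UE weakness in at least one limb, defined as grade 4/5 in ≥ 2 muscles per limb". It then sets the ability-to-test criterion: "Patient must be able to perform 9HPT and TEMPA tests with at least one limb". The second line is not tied to the limb named in the first. The only exclusion in section 4.1.3 for loss of function is "Severe weakness in bilateral upper limbs causing complete loss of function".

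**Scale.** In section 3.3 each TEMPA task is rated from 0 down to -3, and the bottom level is worded "3) not completed, even if any degree of assistance was offered". "Four items are unilateral", and there are "five bilateral tasks". On the total, the section says: "A total score will be determined by adding the scores obtained for both the unilateral and bilateral tasks". The unilateral and bilateral scores are also to be looked at separately for the affected arm.

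**Stability.** Sections 2.1, 3.3.1, 4.9.3 and 4.9.6 treat a change of up to 20% from baseline as stable. Section 4.9.3 adds a review of completion time in the better and worse hand at 15%, 20% and 25%. The plan does not say whether the total, the unilateral score or the worse hand decides that a patient is stable. It sets no minimum baseline score for either arm, and no rule for scores at the floor or for tasks without a completion time.

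**The concern.** The study is meant to learn whether function is kept in impaired arms. An arm that already fails every task has no function left to lose on this scale, yet it is eligible.

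The direction of the effect is what matters. The hypothesis in section 3.3.1 is no change, and section 4.9.6 sets out to report the share of patients who stay stable. There is one group and no control, so nothing offsets a floor effect. Arms that cannot register decline move the result towards the hypothesis without telling us anything about preserved function.

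**Working it through.** The plan has no figure to reproduce: section 4.9.6 says the sample size was not calculated, and no alpha, effect size or standard deviation is given. The check is direct arithmetic.

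**1. Can such an arm enter?** One testable arm is enough (4.1.2), and only bilateral complete loss is excluded (4.1.3). A floor arm can enter if the weakness line is read as grade 4/5 or worse, if other muscles of the qualifying limb are much weaker, or if the other limb supplies the qualifying weakness. So it can enter, although not by every reading.

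**2. Arm-level functional score.** The floor is 4 tasks × -3 = -12. Room to worsen is 0 points, or 0%. The arm is within 20% unless it improves. Arms just above the floor are also constrained: from -11 the largest worsening is 1/11 = 9%, and from -10 it is 2/10 = 20%, which does not exceed 20%.

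**3. Total functional score.** If each unilateral task is rated once per arm, there are 4 × 2 + 5 = 13 ratings and the minimum is -39. (Nine ratings would give -27. Section 3.3 cites a typical range down to -50, which neither count yields, so the scoring needs to be reconciled.) With one arm at -12 and the other at 0:

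| Each bilateral task | Baseline total | Room to -39 | 20% of baseline | Points needed to exceed 20% |
|---|---|---|---|---|
| 0 | -12 | 27 | 2.4 | 3 |
| -1 | -17 | 22 | 3.4 | 4 |
| -2 | -22 | 17 | 4.4 | 5 |
| -3 | -27 | 12 | 5.4 | 6 |

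The patient can be classed as worse in every row. The floor arm nevertheless adds 0.2 × 12 = 2.4 points to the margin. In the last row the better arm can lose 5 of its 12 points (5/27 = 18.5%) and the patient stays stable; 6 points (6/27 = 22.2%) cross the line. On the bilateral tasks alone (-15) the margin would be 3.0, and 4 points would cross it.

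**4. Time.** An arm that completes no task has no baseline time, so a percentage change is undefined. The worse-hand review cannot register progression there, but nothing in the plan says to call the arm stable. Section 4.9.5 deals with missing time points, not with a value that never existed.

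**5. Arm-level functional count.** Let k of 30 patients have the counted arm at the floor, and let p be the true stable share among the rest. The share counted stable is p + (1 - p)k/30. Both k and p are assumptions.

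| p | k = 3 | k = 6 |
|---|---|---|
| 50% | 55% | 60% |
| 60% | 64% | 68% |
| 80% | 82% | 84% |

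Working backwards with k = 6, an apparent 18/30 (60%) becomes 12/24 (50%), and an apparent 24/30 (80%) becomes 18/24 (75%).

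**6. Paired t-test on an arm-level score.** Assume a two-sided 5% level and a standardised change of 0.5 in arms that can change. Setting k of 30 changes to zero lowers power to detect change from 75% (k = 0) to 70% (k = 3) or 64% (k = 6). In a sign test these arms are ties.

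**The case against.** A reader might infer that a patient with a floor arm counts as stabilized whatever happens. The documents do not support that. The hypothesis is stated on the TEMPA score, the total includes the other arm and the bilateral tasks, and every row of the table in step 3 leaves room to worsen by more than 20%. Bilateral tasks at -3 throughout is also a worst case, since -2 is available for partial execution. For the same reason the formula in step 5 does not describe the patient-level percentage on the total score.

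The number affected may be small. Grade 4/5 read literally is mild weakness, joint range must be functional, and severe ataxia and severe spasticity of the arm are excluded. A shift of 4 to 10 percentage points is about the size of one standard error at n = 30 (√(0.5 × 0.5/30) = 9.1 points), in a study that calls itself a pilot.

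The plan also offers some relevant views: separate unilateral and bilateral scores (3.3), better- and worse-hand review (4.9.3), and possible stratification by baseline arm strength (4.2). The analysis named first is a paired t-test, not a percentage.

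All of this limits the size of the problem. It does not remove it. The separate views still contain the floor arms, the stratification is optional, and a systematic shift towards the hypothesis is not excused by being no larger than the sampling error.

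**Conclusion.** The concern holds in a limited form. Eligibility admits an arm at -12, and that arm cannot worsen on its own functional score. In an arm-level functional count it is stable unless it improves. In the total it raises the number of points needed to exceed 20%, by up to 2.4 points before rounding, without fixing the outcome. On time it is non-evaluable, and it would be wrong to read it as stable.

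The figures of 64% and 68% (p = 60%), or 55% and 60% (p = 50%), apply only to an arm-level functional count with 3 or 6 floor arms among 30. The documents give no basis for k, which may be small. The total-score example rests on 13 ratings per patient. The power figures rest on an assumed level and effect size. What does not depend on these assumptions is the direction: towards the study's own hypothesis, in a design with no control group.

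**What to change.** Leave enrolment as it is and change sections 4.9.3 and 4.9.6:

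- Compute arm-level TEMPA stability, functional and time, only for arms that are above the functional floor and have a completed time at baseline, whichever arm qualified the patient.
- Report arms at the floor at baseline (-3 on all four unilateral tasks) separately and outside the percentage stable. It would help to list arms at -10 and -11 beside them, since they cannot exceed 20% worsening either.
- Give the total-score percentage stable with and without patients who have a floor arm.

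The cost is a denominator smaller by a few patients and a less favourable stable percentage. No new data are needed.

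Requiring test ability in the qualifying limb at entry is not recommended. It would narrow the population the protocol sets out to study, and it would miss a floor arm that is not the limb supplying the qualifying weakness.
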